One potential method for increasing provider adoption is through the inclusion of nudges. Nudges are defined as positive reinforcement and indirect suggestions that have a non-forced effect on decision making¹⁷. Recent studies have shown that nudges can be effective in influencing provider decision making. For example, a recent large randomized controlled trial evaluating behavioral interventions found a social comparison “nudge” decreased provider antibiotic prescribing for upper respiratory infections from 19.9% to 3.7%.¹⁹ These results were durable at 3 months.³¹ Another study used a simple poster with the clinicians signature committing to antibiotic stewardship to decrease inappropriate antibiotic prescribing by 20% relative to control.³⁰ Even simply changing the grouping of treatment options has demonstrated the ability to significantly impact provider behavior.³²

In our study, we will assess the impact of adding nudges to an existing CDS tool on efficacy provider adoption. We previously developed a tool, PE CALC, to reduce unnecessary imaging in the diagnosis of pulmonary embolism (PE) in the emergency department (ED). One common test for PE, computerized tomography pulmonary angiography (CTPA), is sensitive and specific for PE; however, it is associated with a median of 10 mSV of radiation, the equivalent of 137 chest x rays.³³ A recent study including 2.5 million Medicare emergency visits found utilization to have increased fivefold between 2000 and 2009 with diagnostic yield declining.³⁴ It is now thought that 1.5% to 2% of all future cancers in the United States may be the result of medical radiation.³⁵ Surveyed emergency providers said that about a fifth of all imaging studies ordered are medically unnecessary,³⁶ with factors including fear of missing a low-probability diagnosis and fear of litigation. Clinical prediction rules address these concerns. Clinical prediction rules are validated tools that quantify the contributions the history, physical and laboratory results make towards a diagnosis, prognosis or treatment response.³⁷ They classify patients into low, intermediate and high probability of PE based on key elements of the history and physical exam, establishing pre-test probability before imaging.

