AIM 2: To conduct iterative usability testing on an evolving prototype of a new tool, “PERK”. This will involve both qualitative and quantitative assessments of ease of use of “PERK”. We will perform “think aloud” and “near live” testing to develop a prototype that will be revised and evaluated.

AIM 3: To evaluate the feasibility, acceptability and preliminary efficacy on provider adoption of a new tool compared to the current tool, in a pilot trial. We will conduct a 6 month pre-post analysis of “PERK” by comparing it to retrospective data from the first 6 months of PE CALC. Our primary feasibility outcome is post-pilot provider satisfaction. Secondary outcomes include stakeholder acceptability.

***H1:** PERK will demonstrate higher rates of provider satisfaction as compared to PE CALC.* Our primary efficacy outcome is increased provider adoption. Secondary outcomes include increased CTPA yield [% of positive tests], and decreased CTPA ordering. ***H2:** “PERK” will demonstrate higher provider adoption as compared to PE CALC.*

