10. ENDPOINTS

- *Describe the primary and secondary study endpoints*
- *Describe any primary or secondary safety endpoints*

The endpoint of this study is provider adoption of the PERK tool. Secondary outcomes include increased CTPA yield [% of positive tests], and decreased CTPA ordering.

Our primary feasibility outcome is post-pilot provider satisfaction.

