In AIM 3, we will conduct a pilot trial to evaluate the feasibility, acceptability, and preliminary efficacy on provider adoption of the new tool, “PERK”, compared to the current PE CALC tool. This will consist of a six month prospective cohort pilot study with a retrospective cohort control group. All full time ED providers at NSUH and LIJMC will be eligible for participation. Training on PERK use will be conducted as a presentation during ED Grand Rounds. This will be led by [name] and a research coordinator. It will last about 30 minutes with three basic components: 1) overview of the evidence supporting tool use, 2) hands-on session to practice using the tool, and 3) question and answer session. Similar educational training was conducted before launching the current tool, PE CALC.

For the pilot study, we will use EHR reporting data to generate a PERK monitoring dashboard. The dashboard will include trigger rates (percentage of ED patients for which the tool triggers), adoption rates (the percentage of times the provider completes the calculator once the tool is triggered), CTPA order rates (percentage of total ED patients for which a CTPA is ordered for the evaluation of PE), and CTPA yield (the percentage of tests ordered to evaluate for PE that are positive for PE).

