For AIM 3, we will determine the feasibility of PERK using post-pilot provider satisfaction surveys, where mean scores for each response on a Likert scale will be reported with standard deviations and 95% confidence intervals. Acceptability will be determined from post-pilot stakeholder interviews with providers, nurses and the ED chairs at both institutions. Preliminary efficacy will be assessed by comparing provider adoption of PERK to provider adoption for the first six months of PE CALC. Providers in the pre- and post- groups will be summarized using descriptive statistics. Provider age, gender, race and type (attending vs. resident vs. physician assistant) will be compared between the two groups using two-sample t-test or Wilcoxon Rank Sum test for continuous variables and Chi-squared or Fisher's exact test for categorical variables. Since the variability of the adoption rate of PERK for each provider depends, in part, on the number of encounters, providers with larger numbers of encounters should carry more weight. Therefore, a weighted two-sample t-test will be used to test the difference in the weighted means of adoption rates between the groups. Weighted least squares linear regression with number of encounters as weight for each observation (provider) will be performed, to see whether there is difference in the adoption rate between the two groups after controlling for provider age, gender, race, type and other confounding variables.

Power Calculations: We expect 150 providers who meet the inclusion criteria to be in each of pre- and post- groups. We also assume the mean adoption rate of the pre group to be 15% with the standard deviation of 10% based on the historical data, and the mean adoption rate of the post- group to be 20%, 25% and 30% with equal standard deviation. With the sample size of 150 in each group, there will be at least 99% power to detect the difference of 5%, 10% and 15% in the mean adoption rates using a two-sided two-sample t-test at a significance level of 0.05. We are aware that the weighted two-sample t-test should be used to calculate the power. However, due to the lack of information about weights, the unweighted two-sample t-test was used instead.

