24. WAIVER OR ALTERATION OF THE CONSENT PROCESS

Complete this section if you are seeking an alteration or complete waiver of the consent process.

- *Describe the possible risks of harm to the subjects involved in this study and explain why the study involves no more than minimal risk to the subject:*
- *Explain why the waiver/ alteration will not adversely affect the rights and welfare of subjects*
- *Explain why it is impracticable to conduct this research if informed consent is required*
- *If appropriate, explain how the subjects will be provided with additional pertinent information after participation. If not appropriate to do so, explain why.*

For AIM 3, in which we will collect pilot data on the feasibility, acceptability, and preliminary efficacy on provider adoption of the PERK tool, we are requesting a waiver of informed consent. A waiver of informed consent will be necessary in order to have the PERK tool activated in the EMR profiles of the providers.

The research involves no more than minimal risks to the subjects: The study as described in the proposal would be considered a minimal risk study because it involves collection of de-identified aggregate data from the EHR at the NSUH and LIJMC Emergency Departments.

The waiver or alteration will not adversely affect the rights and welfare of the subjects: Due to the functionality of the tool, providers will be offered the tool and have the ability to dismiss the tool. Use of the tool will not affect employment status of the providers at the clinical site/hospital/health system. We will hold an information session for providers regarding the research study and their participation.

The research could not practicably be carried out without the waiver: The primary objective of AIM 3 is to assess the feasibility, acceptability, and preliminary efficacy on provider adoption of PERK compared to the current PE CALC tool in a pilot trial. In order to study this, all patients assessed for PE must be included. The decision support is completely computerized and will be done in real time. It would not be possible or practical to obtain consent from every provider in the Emergency Departments of NSUH and LIJMC prior to their use of the PERK.

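### CTPA ordering and yield are compared crudely between two non-concurrent periods, so a modest change in patient mix could mimic or hide the small effect expected from PERK

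*Combined protocol and SAP*

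**What the plan says.** - **Outcome.** Section 10 (Endpoints): "Secondary outcomes include increased CTPA yield [% of positive tests], and decreased CTPA ordering". Section 4, Aim 3, gives the same two secondary efficacy outcomes.
- **Definition.** Section 11, in the Aim 3 dashboard, defines "CTPA order rates (percentage of total ED patients for which a CTPA is ordered for the evaluation of PE". Yield is the share of CTPAs ordered for PE that are positive.
- **Comparison.** Section 4: "We will conduct a 6 month pre-post analysis of “PERK” by comparing it to retrospective data from the first 6 months of PE CALC". Section 11 describes a "six month prospective cohort pilot study with a retrospective cohort control group".
- **Analysis.** Section 12 (Statistical Analysis) gives a weighted t-test and a weighted regression for adoption, with the provider as the unit. The regression compares the two groups "after controlling for provider age, gender, race, type and other confounding variables". No test or model is given for ordering or yield, and no patient-level variable is named.

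**The concern.** The crude order rate mixes two things: who comes to the ED, and how often providers order a CTPA for patients in whom PE is a consideration. PERK can act only on the second. A concurrent control would share the first. A historical control need not, and nothing in the plan corrects for a difference. Yield has a parallel weakness, because it rises or falls with the prevalence of PE among those tested.

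What is at stake is how the two secondary efficacy results are read. The pilot could report less ordering or better yield when only the patient mix changed, or could miss a real reduction. Either would be a poor basis for planning a later trial.

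**Working it through.** **1. The plan's own figures.**
- Power (Section 12): 150 providers per group, SD 10 points, difference 5 points, two-sided 0.05. 5 / (10 × √(2/150)) = 4.33, and 4.33 − 1.96 = 2.37, so power is 99.1%. The stated figure of at least 99% reproduces. It concerns adoption; no figure is stated for ordering.
- Effect among adopters (Section 3): yield rises from 8% to 12%. With PEs found held constant, total tests fall by 1 − 8/12 = 33.3%. Negative tests per positive fall by 1 − (88/12)/(92/8) = 36.2%, close to the stated 37%.

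**2. Expected effect on ordering.** Take the contrast among adopters as causal, and read 15% adoption as the share of work-ups in which the tool is used. If a is adoption and r the reduction with use, tests are proportional to 1 − a·r. The relative change from a = 0.15 is (1 − a·r)/(1 − 0.15·r) − 1.

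| Adoption (Section 12 scenarios) | r = 1/3 | r = 0.37 |
|---|---|---|
| 20% | 0.9333/0.9500 − 1 = −1.8% | −2.0% |
| 25% | 0.9167/0.9500 − 1 = −3.5% | −3.9% |
| 30% | 0.9000/0.9500 − 1 = −5.3% | −5.9% |

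**3. Effect of patient mix alone.** Let s be the share of ED patients with a PE-type presentation, q1 the order rate in them and q0 the rate in all others. The crude rate is s·q1 + (1 − s)·q0. With q1 and q0 fixed, a relative change in s is passed on with multiplier s(q1 − q0)/rate. The documents give none of these inputs. Assumed for illustration: q1 = 20%, q0 = 0.2%, s from 5% to 15%.

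| s | Crude rate | After a 5% relative fall in s | Relative change | Multiplier | Relative fall in s equal to the 1.8%, 3.5%, 5.3% effects |
|---|---|---|---|---|---|
| 5% | 1.190% | 1.141% | −4.2% | 0.83 | 2.1%, 4.2%, 6.3% |
| 10% | 2.180% | 2.081% | −4.5% | 0.91 | 1.9%, 3.9%, 5.8% |
| 15% | 3.170% | 3.022% | −4.7% | 0.94 | 1.9%, 3.7%, 5.6% |

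The multiplier is 1 only if no CTPA is ordered outside PE-type presentations. With s at 10%, a move to 9.5% of visits produces most of the largest expected effect, and an equal rise would hide most of it.

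**4. Yield.** On the same assumptions, with 8% as the yield without the tool, whole-ED yield is 8%/(1 − a/3): 8.4% at 15% adoption, then 8.6%, 8.7% and 8.9% at 20%, 25% and 30%. A relative change in PE prevalence among those tested of about 2% to 6% (8.57/8.42 − 1 to 8.89/8.42 − 1) would do the same. Section 3 itself reports no rise in whole-ED yield with PE CALC.

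**5. Time gap.** Section 3 reports PE CALC results already obtained, and Section 9 starts the Aim 1 interviews in January 2019. PE CALC's first six months therefore ended by about mid-2019 at the latest. A six-month pilot ending in June 2022 (Section 9) starts about January 2022. The gap is at least about 2.5 years. This is an inference, because the launch date is not given, and nothing says that the calendar months match.

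**The case against.** The case for leaving the plan alone has weight. Ordering is a secondary outcome in a pilot of preliminary efficacy, and H1 and H2 concern satisfaction and adoption. Total ED patients is a simple denominator that does not depend on complaint coding, whereas a complaint list misses some CTPAs and is open to coding drift. The dashboard also reports trigger rates, which give a partial view of changing work-up volume. The more basic gaps are the historical control and the absence of any stated analysis of ordering.

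Most of this stands, and it is why the total-ED rate should be kept and the concern held to interpretation. It does not remove the problem. The trigger logic is not described and could differ between the tools. The open-ended reference to other confounders in Section 12 belongs to the adoption model.

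A reader might go further in two ways that the documents do not support:

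- **That Section 24 requires a different denominator.** It says "In order to study this, all patients assessed for PE must be included", but as part of the case for waiving consent. It sets no analysis population, and a total-ED count already includes those patients.
- **That a switch to another test would be wrongly scored as success.** Section 3 does call CTPA "One common test for PE". But the endpoint is "decreased CTPA ordering", and the rationale (radiation, contrast nephropathy, incidental findings) is specific to CTPA. Fewer CTPAs is what the endpoint sets out to measure.

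**Conclusion.** The concern holds as a limit on interpreting the two secondary efficacy outcomes. As planned, a crude before-after difference in ordering or yield cannot be attributed to PERK. The expected reduction in CTPAs is about 1.8%, 3.5% or 5.3% (up to 5.9% with the stated 37%). A relative fall of similar size in PE-type presentations would produce nearly, not exactly, the same change.

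The size rests on taking the adopter contrast as causal, holding PEs constant and reading 15% as a share of work-ups; Section 3 words it as a share of providers. The case-mix figures rest on assumed order rates.

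It would go too far to say that patient mix did change, or that the bias favours PERK: the documents show neither. The primary outcome is also outside this point, because adoption is counted among triggered encounters, not total ED patients. The change is worth making before analysis, at moderate priority.

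**What to change.** Keep the total-ED order rate in Section 11. Add to Section 12:

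- **Standardised comparison.** From aggregate EHR counts of ED patients, CTPAs for PE and positive CTPAs, by age group, sex and triage complaint, compare order rate and yield between periods, standardised to the PE CALC-period mix. For order rate this is Σ w_k × (CTPAs_k / patients_k), where w_k is stratum k's share of ED patients in the PE CALC period. For yield, one option is the standardised positive rate divided by the standardised order rate with the same weights, which avoids conditioning on who was tested.
- **Accompanying measure.** Report the order rate among patients with PE-relevant triage complaints, using the same complaint list in both periods.
- **Interpretation.** Show crude and standardised figures side by side and base conclusions about ordering or yield on the standardised ones. State that standardisation does not remove secular changes in ordering practice, and that these strata are only a rough proxy for PE prevalence among those tested.

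**Cost.** A few more EHR fields and one more set of tables. Complaint coding is imperfect, which is a reason to keep the crude rate alongside. Stratified counts fit the de-identified aggregate data on which Section 24 bases the consent waiver. A patient-level regression might go beyond that description and need a revised submission, so it is not proposed here.

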12. STATISTICAL ANALYSIS

- *Describe how your data will be used to test the hypotheses.*

- *State clearly what variables will be tested and what statistical tests will be used.*
- *Include sample size calculations.*
- *If this is a pilot study, state which variables will be examined for hypothesis generation in later studies.*

For AIM 1, we will perform qualitative analyses of our semi-structured interviews. We will use NVivo software (QSR International, Inc.) for qualitative data storage and organization. Use of computer-assisted techniques improves procedure standardization, enhances completeness, and permits greater flexibility in revising the analysis process. We will code and analyze the transcripts using a modified grounded theory informed by COM-B. In grounded theory, themes are not specified prior to analysis, but our modified approach will use the framework of COM-B to organize emergent themes (e.g., psychological capability, social opportunity). [name] and [name] will develop a codebook reflecting emerging themes after iteratively reading the transcriptions so that triangulation can be assessed and a broader and more complex understanding of the data attained. Using the constant comparative method, additional readings of the transcriptions will lead to the consolidation of these coding schemes until no further refinement is required. Coding discrepancies will be resolved by consensus. Coder agreement will be calculated with Cohen's kappa. In order to improve accuracy, validity, and transferability of the results, respondent validation will be implemented. Participants will be shown an analysis summary and asked to provide feedback if it conforms to their responses during interviews ensuring that the participant meanings and perspectives are accurately represented.

For AIM 2, we will perform qualitative analyses of our “Think Aloud” and “Near Live” usability testing. After all usability testing, the audio recordings of subjects will be transcribed verbatim and linked to screen capture videos. Two independent coders will read the annotated transcripts and watch the corresponding video for each case. All discrepancies in the coding will be resolved by discussion to achieve a consensus. Each coded segment of the transcribed text will be categorized for: (a) the CDS components involved, (b) usability/workflow issues as conveyed through providers’ verbalizations and actions, (c) type of commentary provided by the subject (i.e. “positive”, “neutral” or “negative” commentary). We will perform a thematic analysis of the transcribed audio recordings as recommended by Boyatzis.⁶⁹ Frequencies of codes will be tabulated for each subject. Morae software allows annotation of each of the components being used, time of use and usability theme. During “Near Live” usability testing the onscreen video recordings will be reviewed for time to CDS completion and time spent in workflow components. We will use NVivo software (QSR International, Inc.) for qualitative data storage and organization. We will code and analyze the transcripts using a modified grounded theory informed by COM-B. In grounded theory, themes are not specified prior to analysis, but our modified approach will use the framework of COM-B to organize emergent themes (e.g., psychological capability, social opportunity). [name] and a trained research assistant develop a codebook reflecting emerging themes after iteratively reading the transcriptions. Using the constant comparative method, additional readings of the transcriptions will lead to consolidation of these

coding schemes until no further refinement is required. Coding discrepancies will be resolved by consensus.

For AIM 3, we will determine the feasibility of PERK using post-pilot provider satisfaction surveys, where mean scores for each response on a Likert scale will be reported with standard deviations and 95% confidence intervals. Acceptability will be determined from post-pilot stakeholder interviews with providers, nurses and the ED chairs at both institutions. Preliminary efficacy will be assessed by comparing provider adoption of PERK to provider adoption for the first six months of PE CALC. Providers in the pre- and post- groups will be summarized using descriptive statistics. Provider age, gender, race and type (attending vs. resident vs. physician assistant) will be compared between the two groups using two-sample t-test or Wilcoxon Rank Sum test for continuous variables and Chi-squared or Fisher's exact test for categorical variables. Since the variability of the adoption rate of PERK for each provider depends, in part, on the number of encounters, providers with larger numbers of encounters should carry more weight. Therefore, a weighted two-sample t-test will be used to test the difference in the weighted means of adoption rates between the groups. Weighted least squares linear regression with number of encounters as weight for each observation (provider) will be performed, to see whether there is difference in the adoption rate between the two groups after controlling for provider age, gender, race, type and other confounding variables.

Power Calculations: We expect 150 providers who meet the inclusion criteria to be in each of pre- and post- groups. We also assume the mean adoption rate of the pre group to be 15% with the standard deviation of 10% based on the historical data, and the mean adoption rate of the post- group to be 20%, 25% and 30% with equal standard deviation. With the sample size of 150 in each group, there will be at least 99% power to detect the difference of 5%, 10% and 15% in the mean adoption rates using a two-sided two-sample t-test at a significance level of 0.05. We are aware that the weighted two-sample t-test should be used to calculate the power. However, due to the lack of information about weights, the unweighted two-sample t-test was used instead.

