During the first half of Year 3, we will develop the new PERK tool. In the second half of Year 3, we will recruit for the pilot clinical trial in AIM 3. The new PERK tool will be active for 6 months, and all full-time employed providers working in the emergency department at NSUH and LIJMC will be eligible for participation. We will perform the pilot trial in Year 4. The clinical decision support tool will be integrated into the electronic medical record and will be accessible for all full-time employed emergency department providers (n=150). Providers will be trained on using the tool through 30 minute sessions delivered during emergency department grand rounds. Additional education sessions will be delivered to continue participant engagement over time. In the second half of Year 4, to assess feasibility, providers will be contacted by email to participate in a post-pilot satisfaction survey. Reminder emails to complete the survey will be sent out up to five times. To assess acceptability, providers will be contacted by email to participate in one-time stakeholder interviews. A follow up phone call will be conducted with providers to provide participant information and solicit interest. The pilot trial will end in June 2022. We will complete our analyses in the first quarter of Year 5. The anticipated end date for this grant is August 31st, 2023.

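### PERK's adoption is compared only with PE CALC's launch period, probably about three years or more earlier, so a change between periods in launch-phase adoption cannot be told apart from a PERK effect

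*Combined protocol and SAP*

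**What the plan says.** The comparator is stated consistently. Under Aim 3, section 4 describes a six-month pre-post analysis, "comparing it to retrospective data from the first 6 months of PE CALC". Section 11 calls it a "six month prospective cohort pilot study with a retrospective cohort control group". Section 12 repeats it: preliminary efficacy is judged by "comparing provider adoption of PERK to provider adoption for the first six months of PE CALC".

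Nobody stays on PE CALC. Section 9 makes PERK "accessible for all full-time employed emergency department providers (n=150", and section 5 enrols all eligible providers automatically.

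The main test in section 12 is an encounter-weighted two-sample t-test. A weighted regression then compares the groups "after controlling for provider age, gender, race, type and other confounding variables". Calendar time is not named. No later PE CALC period, time trend or staggered start is planned, and section 12 states no limitation of the historical comparator.

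On timing, section 9 says "We will perform the pilot trial in Year 4" and "The pilot trial will end in June 2022", with PERK active for six months. PE CALC was already in use when the Aim 1 interviews began in January 2019, because section 11 has interviewees graded by how much they used it. Section 11 also notes that comparable training preceded PE CALC's launch.

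**The concern.** H2 credits the difference in adoption to PERK. With one historical window and one current window, the difference also contains whatever else changed between the two periods in how readily these departments take up a newly launched tool. Upward change would be read as a PERK benefit. Downward change would understate or hide a real one.

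The planned precision does not protect against this. The stated power of at least 99% covers sampling error only, and a small standard error makes a small bias look conclusive. Nothing in the planned analysis would show whether such a change took place.

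**Working it through.** **1. The interval (inferred).** Section 9 gives the Aim 1 interviews from January 2019 in Year 1, the pilot in Year 4 ending June 2022, six active months, and a grant end of 31 August 2023.
- If Year 5 ends with the grant, Year 4 runs from September 2021 to August 2022. If Year 1 starts in January 2019, Year 4 is calendar 2022.
- Six active months finishing by June 2022 put go-live between about September 2021 and January 2022, which is 32 to 36 months after January 2019.
- PE CALC launched before January 2019, so the windows start more than 32 to 36 months apart. If its first six months were also complete by then, the gap is at least 38 to 42 months.

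**2. What the analysis can separate.** Every PE CALC observation falls in the earlier period and every PERK observation in the later one. A model with an intercept, a tool indicator and a period indicator has three columns but rank 2. The unspecified confounders in the weighted regression therefore cannot include period. The regression can remove change that arises from measured age, gender, race and provider type. It cannot remove the rest, and the t-test removes none of it.

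**3. The plan's own power figure.** Section 12 gives 150 per group, a pre-group mean of 15% with SD 10%, two-sided alpha 0.05, and "the mean adoption rate of the post- group to be 20%, 25% and 30% with equal standard deviation".
- SE = 10 × √(2/150) = 1.155 points.
- For 5 points the noncentral t on 298 df gives 99.1%. For 10 and 15 points power exceeds 99.9%. The stated figure reproduces.

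**4. Size of drift that matters (illustration; all drift values are assumed).**
- Smallest significant difference = 1.968 × 1.155 = 2.27 points. Spread over three years, that is 2.27/3 = 0.76 points a year.
- Period drift adds to the estimate one for one. A drift of 3 points is 3/5 = 60%, 3/10 = 30% or 3/15 = 20% of the three planned effects.
- With no PERK effect, the probability of a significant result in PERK's favour is 41% for an upward drift of 2 points and 74% for 3 points.
- With a true 5-point effect, a downward drift of 3 points leaves a net 2 points and cuts power from 99% to 41%. For 10 or 15 points, power stays above 99.9%.
- 80% power needs a net difference of 3.245 points. The downward drift tolerated is therefore 5 − 3.245 = 1.8, 10 − 3.245 = 6.8 or 15 − 3.245 = 11.8 points.

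**5. Sensitivity of these figures.**
- Section 5 gives a pool of 86 + 63 = 149 providers, so some probably appear in both windows. If all did, with an assumed correlation of 0.5, the true SE would be 10 × √(2 × 0.5/150) = 0.816. Against the same 2.27-point threshold, 41% becomes about 37% and 74% about 81%.
- The weights are unknown. If they had an assumed coefficient of variation of 1 and the SD did not depend on volume, the effective number per group would be 150/(1 + 1) = 75. The SE would be 10 × √(2/75) = 1.63 and the smallest significant difference about 1.96 × 1.63 = 3.2 points.

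**The case against.** The strongest reply is that comparing launch with launch is deliberate and sensible. It matches the novelty phase and, with similar training beforehand, the launch effort. The documents openly call it pre-post with a retrospective control, and the result preliminary. That stands, and it is why the planned test should be kept.

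It also corrects a tempting inference. A reader might conclude that any movement in PE CALC adoption after its first six months biases H2. It does not. Fatigue with PE CALC, or its novelty wearing off, is ageing of that tool and does not enter a launch-against-launch contrast. Only a difference between the two periods in launch-phase adoption does. Nor is every such difference absorbed, because the regression can take out the part due to measured provider mix.

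A second objection also stands: a pre-switch PE CALC window does not measure the bias. It differs from PE CALC's launch window by ageing and by period together. If adoption fell after launch, comparing PERK with that window would flatter PERK. The supporting contrast has a different bias rather than none, and it cannot say by itself how much of the planned estimate is drift.

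Finally, the drift values are assumed and the interval is inferred. Both are true, and they limit what can be claimed about size. They do not affect the aliasing, which follows from the design. The pilot label lowers the weight of the result, but H2 still carries a formal test and a power calculation.

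**Conclusion.** The concern holds in a limited form. Period is aliased with tool, and neither planned analysis can remove a between-period change in launch-phase adoption beyond measured provider mix. The windows probably start about three years or more apart.

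A reader might infer from the 41% and 74% that a false positive is likely. The documents do not support that, since they give no drift in either direction. The percentages show only how small a drift would matter on the plan's unweighted inputs with independent groups; weighting and provider overlap would change them. The significance verdict is exposed mainly when the true effect is nil or near 5 points. The size of the estimate is exposed throughout.

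This is a worthwhile, inexpensive improvement, not a defect that invalidates the pilot.

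**What to change.** Keep the launch-against-launch comparison as the planned test and add to section 12:

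- A supporting analysis against PE CALC adoption in the six months just before PERK's actual go-live, using section 11's definition (the share of tool triggers in which the calculator is completed). Alternatively, if monthly data run up to go-live, a segmented provider-month model with a time trend, a PERK step and clustering by provider.
- Both contrasts, each with a 95% confidence interval.
- A statement that the pre-switch contrast removes most calendar drift but contains PERK's launch novelty and retraining and PE CALC's ageing. The two contrasts therefore have different biases, and neither isolates the nudges.
- Attribution of the result to the PERK launch, meaning tool plus training.

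The cost is a wider EHR extraction and some analysis time. Two checks come first. Section 6 shows only that providers can be identified by their PE CALC use, so provider-level triggers and completions up to go-live must be confirmed as retrievable. The wider window must also be covered by the Aim 3 waiver, whose minimal-risk case in section 24 rests on de-identified aggregate data. If later PE CALC data cannot be obtained, section 12 should state the limitation of the historical comparator.
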